5.1.2 Statistical inference

To gauge for presence of evaluation bias, inter-rater agreement will be determined using Cohen's kappa. This test measures the extent to which physicians concur when assessing for presence of OIWS using the DSM-5 criteria. A kappa of ≥ 0.61 is indicative of good inter-rater agreement (70).

For secondary outcomes, baseline, weaning and change in cortisol levels will be compared between patients positive and negative for OIWS. A Student's t-test or a Wilcoxon signed rank test will be used. The test will be determined based on distribution and sample size.

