4.1 Study design

Multicenter Prospective Observational Open Cohort Study

The clinical presentation of OIWS is poorly described in the adult ICU population. The descriptive study design aims to identify signs and symptoms of OIWS in the prospect of developing a validated bedside screening tool. The prospective approach will enable collection of all relevant information while limiting missing data and assessing for potential confounding variables.

Throughout the study, investigators will be blinded to the diagnosis of OIWS to reduce evaluation bias and increase internal validity. Additionally, on one occasion for each patient, OIWS evaluation will be performed by two physicians, allowing for inter-rater reliability. This will ensure accurate OIWS diagnosis and reduce information bias. Following transfer to the ward, one additional data collection will be performed to optimize OIWS detection.

The study will be conducted in two hospitals of the McGill University Health Centre (MUHC) with different ICU populations, hereby increasing the external validity of the results. The MGH is a Level I trauma center, whereas the RVH treats surgical and medical patients. Furthermore, a multicentric approach will increase the sample size and the likelihood of describing the syndrome adequately.

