Once the patient begins the targeted opioid weaning of $\geq 10\%$, investigators will perform evaluations daily between 10am and 2pm. These evaluations will consist of using pre-tested data collection sheets to record signs and symptoms of possible OIWS, opioid doses, administered medications, laboratory values and other clinical data such as the RASS, CPOT and CAM-ICU scores. Data collection will be based on subject observation and interview when possible, nurse assessments, medical charts and laboratory results. Serum cortisol levels will be measured on the first day of opioid weaning (± 2 hours from dose decrease) and on the day patient is transferred to the ward or 72 hours from start of weaning whichever occurs first.

Once a weaning episode is identified, the physician collaborator will be contacted to perform daily DSM-5 evaluations. DSM-5 evaluations will be placed in opaque envelopes and investigators will be blinded to the results throughout the study. Additionally, for each patient, at least one inter-rater DSM-5 evaluation between 2 physician collaborators will be performed in order to assess interrater reliability. The two evaluations will be done within 2 hours of each other to minimize time-related discrepancies.

If opioid weaning is unsuccessful and opioid dose is re-increased, the subject will continue to be observed, however daily evaluations will only resume at the next weaning episode. Daily follow-up ends on day of transfer to the ward. One additional data collection and DSM-5 evaluation will be performed on the same day within 24 to 96 hours following transfer. Follow up ends 14 days after initial opioid weaning if patient remains in the ICU or if patient dies.

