5.2 Sample size

Based on our experience with the WAAICUP studies, 88 patients were eligible to participate in the study in an 8-month period, of which around 50 consented (22). We thus aim to recruit 50 patients based on the feasibility of these previous studies.

6. Advantages and limitations

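### A kappa near 0.61 from about 50 pairs does not by itself show good agreement, and at any sample size kappa measures agreement between physicians, not bias or accuracy.

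*Combined protocol and SAP*

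**What the plan says.** Section 5.1.2 gives the purpose and the statistic together: "To gauge for presence of evaluation bias, inter-rater agreement will be determined using Cohen's kappa". It then says that a kappa of at least 0.61 "is indicative of good inter-rater agreement", citing a reference on kappa. It plans no confidence interval, no positive or negative agreement, and no comparison of how often each physician rates positive.

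Section 4.1 describes the paired rating as follows: "on one occasion for each patient, OIWS evaluation will be performed by two physicians, allowing for inter-rater reliability". The next sentence claims: "This will ensure accurate OIWS diagnosis and reduce information bias". Section 6.1 also gives one paired occasion per patient. Section 4.5 is looser: "for each patient, at least one inter-rater DSM-5 evaluation between 2 physician collaborators will be performed".

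The number of patients comes from section 5.2: "We thus aim to recruit 50 patients based on the feasibility of these previous studies". Section 5.1.1 adds that when the two physicians disagree, the positive rating is the one kept.

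**The concern.** There are two separate faults.

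The first is precision. The label is attached to a point estimate. With about 50 pairs and few positive ratings, kappa rests on a handful of patients and can land above 0.61 when true agreement is only moderate.

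The second is meaning, and it does not depend on sample size or prevalence. Kappa describes how far two physicians concur. They can concur and both be wrong. They can also differ systematically and still pass the threshold.

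The DSM-5 rating defines the W+ and W- groups, and so both the symptom comparison and the cortisol comparison. Kappa is the only quantitative check planned on that rating. The rule for discordant pairs makes the direction of disagreement important: a physician who over-calls adds withdrawal episodes directly, and kappa alone does not show this.

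**Working it through.** **Inputs**
- Pairs, n: about 50, from 50 patients (section 5.2) with one pair each (sections 4.1 and 6.1). Section 4.5 allows more than one, so 50 is the planned minimum if every patient is paired.
- Threshold: 0.61 (section 5.1.2).
- Positive rate among paired ratings, p: not given. The only prospective adult figure is 16.7% (sections 1 and 2), and it is per patient. The rate on a paired day is lower if not every day of a withdrawal-positive patient is positive. The retrospective range of 19.7% to 100% in section 2 points the other way. I take p from 5% to 50%; 50% is the best case for precision.
- Confidence level: not stated; 95% two-sided assumed.

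The plan gives no precision for kappa and its sample size is a feasibility figure, so there is no figure of the plan's own to reproduce.

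**Interval around an observed 0.61.** When both physicians have positive rate p, the large-sample variance is

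Var(κ) = [(1 − κ)/n] × [(1 − κ)(1 − 2κ) + κ(2 − κ)/(2p(1 − p))]

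At κ = 0.61, p = 0.167, n = 50:
- (1 − κ)/n = 0.39/50 = 0.0078
- (1 − κ)(1 − 2κ) = 0.39 × (−0.22) = −0.0858
- κ(2 − κ)/(2p(1 − p)) = 0.8479/0.2782 = 3.048
- Var = 0.0078 × 2.962 = 0.0231, so SE = 0.152
- 95% CI = 0.61 ± 1.96 × 0.152 = 0.31 to 0.91

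Each physician would be expected to give 50 × 0.167 = 8.35 positive ratings.

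**Chance of reaching 0.61 when true agreement is lower.** For 50 pairs with P(both positive) = p² + κp(1 − p) and equal positive rates, the probability that the observed kappa is at least 0.61 is:

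| Assumed p | 95% CI at observed 0.61 | Labelled good if true κ = 0.40 | Labelled good if true κ = 0.50 |
|---|---|---|---|
| 5% | 0.10 to 1.00 (capped) | 24% | 37% |
| 10% | 0.24 to 0.98 | 16% | 31% |
| 16.7% | 0.31 to 0.91 | 10% | 24% |
| 30% | 0.37 to 0.85 | 6% | 19% |
| 50% | 0.39 to 0.83 | 4% | 16% |

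**What would be enough.** At p = 0.167 and an observed κ = 0.83, the same formula gives SE = 0.107 and a lower limit of 0.83 − 0.21 = 0.62. So about 0.83 or more puts the lower limit at 0.61.

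**One-sided disagreement.** Take 50 pairs: 5 both positive, 0 positive for A only, 5 positive for B only, 40 both negative.
- Observed agreement = 45/50 = 0.90
- Chance agreement = (5/50)(10/50) + (45/50)(40/50) = 0.02 + 0.72 = 0.74
- κ = (0.90 − 0.74)/(1 − 0.74) = 0.615

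The threshold is met, yet B rates twice as many positives as A and all five disagreements run one way (exact McNemar p = 2 × 0.5⁵ = 0.0625).

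**Shared error (assumed figures, for illustration).** Let true prevalence be 16.7%. Let the same misleading cue make both physicians see 20% of true negatives as positive, and let each also err independently 5% of the time.
- Apparent prevalence = 0.167 + 0.20 × 0.833 = 0.3336
- Each physician's positive rate = 0.95 × 0.3336 + 0.05 × 0.6664 = 0.350
- P(both positive) = 0.95² × 0.3336 + 0.05² × 0.6664 = 0.3027
- κ = (0.3027 − 0.350²)/(0.350 × 0.650) = 0.79
- Share of positive ratings that are true = 0.95 × 0.167/0.350 = 45%

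Kappa is comfortably above 0.61 while fewer than half of the positive ratings are correct.

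**The case against.** The study is descriptive, and section 6.2 says so. The 0.61 cut-off is a cited label, and no analysis, diagnosis or exclusion depends on passing it. Section 5.1.2 itself says, correctly, that kappa measures how far physicians concur, and section 4.6 admits that the DSM-5 is not validated in the ICU. All of this stands, and it keeps the point minor. It does not remove it: section 6.2 does not extend its caution to kappa, a descriptive estimate still needs its uncertainty, and sections 4.1 and 5.1.2 make positive claims about accuracy and bias.

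The positive rates are also assumptions, so the results are shown as a range in both directions. At 16.7%, the rule refuses the label to a true kappa of 0.40 about 90% of the time.

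A reader might infer that 50 pairs can never show good agreement. The documents do not support that: a high enough observed kappa would. Nor do they support treating the bias fault as a result of small numbers, since more pairs would not cure it.

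A strict rule that the lower limit must exceed 0.61 is one convention among several. With 50 pairs it would often withhold the label from reliable raters: for 80% power at a true kappa of 0.80 and 16.7% positive, about 145 pairs are needed.

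**Conclusion.** The point holds in two limited parts.

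First, reading a point kappa at or near 0.61 as good agreement is unsupported with about 50 pairs. The 95% lower limit is about 0.31 at an assumed 16.7% positive rate, and no higher than 0.39 at the most favourable rate. This rests on the assumed positive rate, equal rates for the two physicians, and one pair per patient. Missed pairs would widen the interval (0.28 to 0.94 with 40 pairs at 16.7%). Extra pairs within a patient would be correlated and would add less than their number suggests.

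Second, the wording that kappa gauges evaluation bias and that double rating secures an accurate diagnosis is wrong whatever the sample size or prevalence.

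The point is minor in severity. It affects how the reliability of the reference diagnosis is reported and does not call for a larger sample.

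**What to change.** In section 5.1.2:
- Report the full 2x2 table, kappa with a 95% confidence interval, and positive and negative agreement. If any patient contributes more than one pair, allow for clustering in the interval.
- Where a first (primary) and a second rater can be identified, report each one's positive rate. The documents do not define these roles. Without them, a difference between raters has no clear direction.
- Keep the 0.61 label if wanted, but interpret it in light of the interval.
- Replace the purpose clause ("To gauge for presence of evaluation bias") with a statement that kappa measures agreement between physicians.

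In section 4.1, replace the claim that double rating ensures an accurate diagnosis with the same statement. Make sections 4.1, 4.5 and 6.1 agree on whether there is one pair per patient or at least one.

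The cost is a few lines of analysis and text, with no new data. The downside is that the reliability claim will probably be weaker.

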The literature on opioid dependence has consistently demonstrated elevated levels of cortisol (12, 25-38) and catecholamines (12, 39-43) during the acute withdrawal phase. Human and animal

models postulate that long-term use of opioids induces hypoadrenalism through impairment of the hypothalamic-pituitary-adrenal (HPA) axis. Opioid withdrawal leads to marked elevations of cortisol as a result of excess ACTH secretion (26, 32, 35). This HPA activation persists following normalization of the adrenergic system, which led some authors to conclude that cortisol is a more sensitive indicator of opioid withdrawal than catecholamines (30, 32). A small study by Higgins et al. on 5 non-dependent subjects assessed acute opioid withdrawal after a single dose of morphine and observed a dose-dependent increase in cortisol levels when subjects were subsequently injected with naloxone (28). Despite the clinical relevance, several limitations reduce the applicability of those results to our study population, mainly the selection of opioid-dependent subjects and rapid induction of withdrawal – through injection of naloxone or abrupt cessation of opioid with support medications such as alpha₂-agonists. Since our subjects are mostly opioid-naive prior to hospitalization and will be gradually weaned off their opioids, the magnitude of increase in cortisol levels will likely be lower.

As for catecholamines, serum epinephrine and norepinephrine appear to increase rapidly following opioid withdrawal in numerous animal and human studies (12, 39-43). However, in contrast with cortisol, catecholamine levels decrease shortly following acute withdrawal. In a study of subjects undergoing rapid opioid detoxification, catecholamine levels peaked two hours following naloxone administration (12). A gradual opioid weaning as often seen in clinical practice is unlikely to be recognized through measurement of serum catecholamines.

3. Research objectives

Research question

What are the signs and symptoms of opioid-associated iatrogenic withdrawal syndrome (OIWS) in the adult ICU population?

Primary objective

To identify specific signs and symptoms of OIWS in mechanically ventilated adult ICU patients receiving at least 72 hours of regular opioids at the Montreal General Hospital (MGH) and the Royal Victoria Hospital (RVH) from February to October 2018

Secondary objective

To determine if the presence of OIWS is associated with an increase in serum cortisol.

4. Methods

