4.4.2 Secondary outcome variables

Both serum cortisol levels will only be measured in patients not receiving exogenous corticosteroids.

Independent variables

- **Basal serum cortisol level** (quantitative continuous)
 - Measured \pm 2 hours from the start of opioid weaning
- **Weaning serum cortisol level** (quantitative continuous)
 - Measured on the day of transfer to ward or after a maximum of 72 hours after start of weaning, at the same time of day as the first measure, whichever occurs first.
- **Change in serum cortisol levels** (quantitative continuous)
 - Difference between weaning and basal serum cortisol levels

Confounding variables

- **Timing of sample in hh:mm** (quantitative continuous)
 - Cortisol is secreted in a diurnal pattern (53)
 - Serum cortisol samples will be taken at the same time of day
- **Presence of primary adrenal insufficiency** (qualitative nominal - dichotomous)
 - According to past medical history in medical chart
 - Patients with this condition may present with hypocortisolemia and receive exogenous corticosteroids, which may confound serum cortisol assays
- **Presence of acute illness** (infection, trauma, surgery, illness) (qualitative nominal)
 - According to APACHE II score at ICU admission
 - Cortisol has been studied as a marker of severity of disease, with higher levels associated with worse prognosis. This association appears to be stronger during the first two days of admission (54)
 - May thus increase cortisol levels depending on severity of disease (53)

- May also provoke transient adrenal insufficiency (53)
- **Presence of septicemia or septic shock** (qualitative nominal - dichotomous)
 - Diagnosis of sepsis will be noted according to medical chart
 - Sepsis causes relative adrenal insufficiency in up to 30 to 70% of patients, which may confound results (55-57)
- **Medications (ketoconazole, spironolactone, dopamine agonists, etc.)** (qualitative nominal)
 - May reduce cortisol production (53)

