5.1 Statistical analysis

5.1.1 Descriptive statistics

Demographic and clinical characteristics of patients who developed OIWS will be compared to those who did not. Categorical variables will be presented as proportions. For continuous variables, means and standard deviations will be computed for normal distributions whereas medians (interquartile range) will be used for non-normal distributions.

For the primary outcome, episodes will be compared between the withdrawal positive (W+) group and the withdrawal negative (W-) group. Every day on which the DSM-5 is positive is equivalent to an episode of withdrawal, whereas a negative DSM-5 counts as an episode in which no withdrawal was observed. Patients who are positive for at least one episode of withdrawal make up the W+ group, whereas those who did not have a single episode of withdrawal make up the W- group, thus eliminating crossover. If a single patient experiences multiple days of withdrawal, s/he will account for multiple episodes in the study. Signs and symptoms will be tallied per episode and compared between the two groups. The results will be presented as proportions (i.e. incidence of symptom per total episodes). In the event of a discordant inter-rater evaluation, only the positive result will be taken into account.

For the secondary outcome, serum cortisol levels and changes in serum cortisol levels are continuous variables and therefore descriptive statistics will be used as stated above, depending on the distribution.

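### The cortisol comparison is between independent patient groups, but the only non-parametric test named for it (Wilcoxon signed rank) is for paired or one-sample data

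*Combined protocol and SAP*

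**What the plan says.** The secondary objective in section 3 is "To determine if the presence of OIWS is associated with an increase in serum cortisol". To serve it, section 5.1.2 says that "baseline, weaning and change in cortisol levels will be compared between patients positive and negative for OIWS". It then offers two tests, a Student's t-test or the signed rank test ("Wilcoxon signed rank test will be used"), with the choice to depend on distribution and sample size.

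Section 5.1.1 describes the patient groups. In general terms: "Demographic and clinical characteristics of patients who developed OIWS will be compared to those who did not". For the primary outcome: "Patients who are positive for at least one episode of withdrawal make up the W+ group", and patients with no positive day form the W- group, so nobody belongs to both.

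Section 4.4.2 defines the cortisol data. There is a basal sample within 2 hours of the start of weaning and a weaning sample, "Measured on the day of transfer to ward or after a maximum of 72 hours after start of weaning", whichever comes first. The change is the difference between the two, one value per patient. Also, "Both serum cortisol levels will only be measured in patients not receiving exogenous corticosteroids".

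Section 4.5 has DSM-5 evaluations run daily in the ICU for up to 14 days after the first weaning, with one more 24 to 96 hours after transfer to the ward.

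**The concern.** The comparison is between two sets of patients. A signed rank test needs either two measurements on the same unit or a single sample of differences. Section 5.1.2 plans no within-patient basal-to-weaning contrast to which it could apply, and no section describes matching. The wording may well be a slip for rank sum.

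These are the only between-group hypothesis tests that the plan names, and they serve its only secondary objective. Because distribution and sample size decide the choice, small or skewed groups are exactly what would lead the analyst to the unsuitable option. The t-test is not described as independent-samples either, so the text does not rule out a paired reading of the whole sentence.

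There is also a lesser timing question. DSM-5 evaluation goes on after the second blood draw. If any positive day makes a patient positive for the cortisol comparison, some positive patients may have a weaning cortisol drawn before withdrawal was first recorded.

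**Working it through.** **Which test fits the comparison**

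- Groups: OIWS-positive v OIWS-negative patients (5.1.2). They are disjoint (5.1.1) and unmatched.
- Data: one basal value, one weaning value and one change value per patient (4.4.2).
- Tests that compare two independent groups: unpaired t-test, rank-sum test.
- What signed rank can test: whether paired differences, or a single sample, centre on zero. On the change scores, that is overall change, not a group difference.

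**Group sizes, for illustration**

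The plan has no power calculation to reproduce. Its target of 50 comes from earlier recruitment (section 5.2: 88 eligible, about 50 consenting, 50/88 = 57%). With the 16.7% incidence cited in section 1:

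- Expected positives = 50 × 0.167 = 8.35, so about 8 v 42.
- Binomial 95% range for positives: 4 to 14.

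Groups of 8 and 42 cannot be paired, so a between-group signed rank test cannot be computed.

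**What pooled signed rank would do**

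Simulation with normal change scores, unit SD, 8 v 42, two-sided 5% and 4,000 runs. The changes are assumed.

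| Change in positives / negatives | Rank-sum rejects | Signed rank, all patients, rejects |
|---|---|---|
| 0 / 0 | 4.4% | 5.1% |
| 0.5 SD / 0.5 SD (no group difference) | 3.9% | 92.5% |
| 1 SD / 0 | 68.5% | 15.5% |

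The pooled signed rank test reacts to a change common to both groups and responds weakly to a difference between them.

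**Timing**

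- Second sample: day of transfer or 72 h, whichever is first (4.4.2, 4.5).
- Last DSM-5 evaluation: up to day 14 in the ICU, or 24 to 96 h after transfer (4.5).
- For a patient still in the ICU, the first positive day can therefore fall up to 14 − 3 = 11 days after the sample.

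Let f be the share of positive patients first positive after the second sample. Let r be the share of the full cortisol difference that these patients already carry at that sample. The expected difference, as a fraction of the full one, is 1 − f(1 − r). The documents give neither f nor r, so both are assumed:

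| f | r = 0 | r = 0.5 | r = 1 |
|---|---|---|---|
| 25% | 75% | 87.5% | 100% |
| 50% | 50% | 75% | 100% |

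Over these values the loss runs from none to half. The basal comparison is not affected, since that sample is taken at the start of weaning in everyone.

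**Precision if late-onset patients are left out**

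95% CI half-width in SD units = t(0.975, n1 + n2 − 2) × √(1/n1 + 1/n2):

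- 8 v 42: 2.011 × 0.386 = 0.78
- 6 v 42 (f = 25%): 2.013 × 0.436 = 0.88
- 4 v 42 (f = 50%): 2.015 × 0.523 = 1.05

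Fewer than 50 patients may be sampled, because those on exogenous corticosteroids are not. If 40 are sampled (assumed, 7 v 33), the half-width before any exclusion is 0.84; if 30 (assumed, 5 v 25), it is 1.00.

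**The case against.** The best defence of the test sentence is that it is a naming slip without practical effect. The intended comparison is clear, the t-test is available, and a signed rank test between groups of unequal size would fail at the keyboard. Section 6.1 calls the cortisol work exploratory, and section 6.2 says that the analyses are mainly descriptive and that the sample was not sized for significance. All of this limits the consequence. It does not make the sentence right: the named test cannot do the stated job, and nothing elsewhere in the document corrects it. A reader might infer that the whole cortisol analysis is invalid. The documents do not support that, because a Student's t-test can be the two-sample test and rank sum is an obvious substitute.

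On timing, the objection is stronger. Section 5.1.1 introduces the rule of at least one positive day for the primary outcome. Using it for cortisol is a reasonable inference, given the general patient-level split in the same section, but it is not stated. Section 2 says that symptoms can begin within 12 hours of stopping opioids, so many cases could precede a 72-hour sample. It also reports the conclusion of some authors that "cortisol is a more sensitive indicator of opioid withdrawal than catecholamines", and weaning has begun by the second draw, so late-onset patients may already show a rise. On the other side, section 6.1 values the ward visit because OIWS may appear after transfer. So late onset is possible, but its frequency and effect are open.

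A reader might also infer that the cortisol difference is materially diluted and that late-onset patients should be counted as OIWS-negative. The documents support neither step. Relabelling would put patients who do develop OIWS into the comparison group, including for the basal level, where there is no timing problem. It would also widen the interval, and it would lower power if those patients already carry much of the effect.

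**Conclusion.** The test named is wrong as written, and this can be said with high confidence from the text alone. The simulation only illustrates the direction of the error; its group sizes rest on the cited 16.7% incidence, and its effect sizes and normal distribution are assumptions. The consequence is modest, but the sentence should be corrected.

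The timing point is a minor addition. Positive patients can be first positive after the second sample, and the plan does not say which DSM-5 evaluations define status for cortisol. The effect is unknown and may be zero, so it justifies reporting and a sensitivity analysis, not a new main-analysis definition.

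**What to change.** In section 5.1.2, replace the test sentence with: *Groups will be compared with an independent-samples t-test or a Wilcoxon rank-sum (Mann-Whitney) test.* Keep signed rank only if a within-patient basal-to-weaning comparison is wanted, and then state that comparison separately.

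Add: *The number of OIWS-positive patients first positive after the second cortisol sample will be reported. A sensitivity analysis of the weaning and change comparisons will leave these patients out.* The basal comparison stays as planned, and late-onset patients are not relabelled as negative in the main analysis.

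The cost is one corrected phrase and two added sentences, with no new samples or visits. The sensitivity analysis will be less precise: with 8 v 42 at the start, the half-width grows from 0.78 SD to 0.88 SD or 1.05 SD if two or four positive patients drop out.

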 - Presence of renal replacement therapy according to medical chart (qualitative nominal - dichotomous)
 - Drug accumulation may occur when renal excretion is decreased, minimizing OIWS
- **Level of hepatic dysfunction upon ICU admission**
 - Severity of hepatic dysfunction as calculated by the Child-Turcotte-Pugh score at ICU admission (qualitative ordinal)
 - Drug accumulation may occur when hepatic metabolism is decreased
- **Presence of ECMO** (qualitative nominal - dichotomous)
 - Collected daily according to medical chart
 - Patients on ECMO may require higher fentanyl doses due to sequestration of lipophilic drugs and increased volume of distribution (49)
- **Cumulative opioid dose preweaning** (quantitative continuous)
 - Cumulative opioid dose in fentanyl equivalents ($\mu\text{g/kg}$) according to medication administration record (MAR) from time of start of opioids during ICU admission
 - Higher cumulative opioid doses have been associated with increased risk of IWS in ICU patients (8)
- **Duration of continuous opioid administration preweaning** (quantitative continuous)
 - Time in hours according to MAR or patient flow sheet
 - Prolonged opioid exposure has been associated with an increased risk of IWS in ICU patients (4, 8, 13-15)
- **Rate of opioid weaning > 10% from previous stable dose** (quantitative continuous)
 - Calculated in % according to MAR or patient flow sheet
 - Continuous infusion: perfusion rate over previous 4h
 - Continuous intermittent administration: total dose over previous 12h
 - Rapid tapering or abrupt discontinuation of opioids has been associated with increased risk of IWS in ICU patients (7, 20)
- **Presence of clonidine, beta-blockers or antidepressants prior to ICU admission** (qualitative nominal - dichotomous)
 - The agent and whether it was prescribed in ICU will be noted according to the medication reconciliation chart at admission
 - These medications may cause withdrawal when discontinued
- **Occasional use of prescribed opioids prior to ICU admission** (qualitative nominal - dichotomous)
 - Agent (qualitative nominal) and daily doses in fentanyl equivalents ($\mu\text{g/kg/day}$) (quantitative continuous) will be noted according to medication reconciliation chart at admission
 - Chronic opioid users are excluded from the present study (as indicated in exclusion criteria)

- **Prior history of substance abuse** (qualitative nominal - dichotomous)

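### The unadjusted cortisol comparison leaves out pre-wean opioid exposure, so a difference by OIWS status, most directly in basal cortisol, could reflect exposure rather than withdrawal

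*Combined protocol and SAP*

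**What the plan says.** Section 3 makes it the secondary objective to find out whether OIWS goes with a rise in serum cortisol. Section 5.1.2 states that "baseline, weaning and change in cortisol levels will be compared between patients positive and negative for OIWS" and that "A Student's t-test or a Wilcoxon signed rank test will be used". It describes no regression, stratification or matching.

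Section 4.4.2 times the basal sample within 2 hours of the start of weaning. The second sample is taken at ward transfer or at most 72 hours after weaning starts. The confounders listed there are sample time, primary adrenal insufficiency, acute illness, sepsis, and an entry beginning "Medications (ketoconazole, spironolactone, dopamine agonists, etc". Opioid dose and duration are not named.

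Section 4.4.1 records cumulative opioid dose before weaning (fentanyl equivalents, µg/kg) and duration of administration, under the primary outcome only. It gives the reason for recording dose: "Higher cumulative opioid doses have been associated with increased risk of IWS in ICU patients". It says the same of prolonged exposure.

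On mechanism, the Biomarkers part of section 2 reports that human and animal "models postulate that long-term use of opioids induces hypoadrenalism through impairment of the hypothalamic-pituitary-adrenal (HPA) axis", and then: "Opioid withdrawal leads to marked elevations of cortisol as a result of excess ACTH secretion".

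**The concern.** A confounder of the cortisol comparison is something that influences both cortisol and OIWS status. The plan's text ties pre-wean ICU opioid exposure to OIWS risk and, more tentatively, to cortisol. Exposure is nevertheless missing from the list of cortisol confounders and from the test.

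If OIWS-positive patients received more opioid before the wean, and that exposure lowers cortisol, their basal level would be lower even if OIWS had no relation to cortisol. The weaning and change values could be affected as well. Section 6.1 presents cortisol as a possible biomarker of OIWS, and a crude difference could not separate a marker of withdrawal from a marker of how much opioid the patient had received.

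**Working it through.** **The plan's own figures.** The target of 50 is a feasibility number: about 50 of 88 eligible patients consented earlier (50/88 = 56.8%). The plan gives no alpha, power, SD or effect size, so there is no power figure to reproduce. Its only prospective adult incidence is 16.7%, or 0.167 × 50 = 8.35, about 8 OIWS-positive patients. Cortisol is not measured in patients on corticosteroids, so the sampled number will be smaller if any patient receives them.

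**Which cortisol value is affected.** Let exposure E lower basal cortisol by s·E, and let a fraction r of that suppression lift by the second sample. Then:
- basal: −s·E
- weaning: −(1 − r)·s·E
- change: +r·s·E

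Basal cortisol is affected whenever s > 0. At r = 0 the weaning value is lowered equally and the change is unaffected. At r = 1 the weaning value is unaffected and the whole effect sits in the change. If suppression deepens (r < 0), the change is biased downward. The documents give neither s nor r.

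**Size for the change score, if the dose–change correlation is positive.** Assumptions: 42 sampled patients, 16.7% OIWS (42 × 0.167 ≈ 7), a normal exposure score, odds ratio (OR) for OIWS of 1.5 to 2.5 per SD of exposure, correlation ρ between exposure and cortisol change of 0.2 to 0.6, no true OIWS effect, two-sided 5% test. Only the 16.7% is documented.

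These odds ratios put the mean exposure of OIWS-positive patients above that of OIWS-negative patients by d = 0.40, 0.65 and 0.82 SD. The expected spurious difference is ρ × d, for example 0.4 × 0.65 = 0.26 SD. A simulation with 20,000 runs per cell gave the false-positive rates of the unadjusted t-test:

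| OR (d) | ρ = 0.2 | ρ = 0.4 | ρ = 0.6 |
|---|---|---|---|
| 1.5 (0.40) | 0.08 SD, 5.6% | 0.16 SD, 6.5% | 0.24 SD, 8.8% |
| 2.0 (0.65) | 0.13 SD, 6.2% | 0.26 SD, 9.5% | 0.39 SD, 15.0% |
| 2.5 (0.82) | 0.16 SD, 6.6% | 0.33 SD, 12.0% | 0.49 SD, 21.6% |

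Six of the nine cells are below 10%. The top corner came out between 21% and 22% in repeated runs.

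For scale, the standard error of a 7 versus 35 comparison is √(1/7 + 1/35) = 0.41 SD. The spurious difference exceeds that in one cell only.

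**With exposure as a covariate.** In a linear model of change on OIWS and exposure, the mean difference is within 0.01 SD of zero and the rejection rate is 4.7% to 5.3% in every cell. The average standard error is 0.35 to 0.45 SD, against 0.42 to 0.43 SD unadjusted, so precision is seldom worse.

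**Sensitivity.** Stronger assumptions (8 versus 42 patients, d = 0.5 to 1.2, within-group ρ = 0.3 to 0.7) give 0.15 to 0.83 SD and 6.7% to 56% unadjusted, and about 5% adjusted. The spread shows how far the result depends on inputs that the documents do not supply.

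**The case against.** The strongest objection is that the link from exposure to a cortisol rise without withdrawal is not in the documents. Section 2 attributes the rise to withdrawal itself. It words suppression as postulated and for long-term use, and expects a smaller rise in these mostly opioid-naive, gradually weaned patients. Section 4.3.2 excludes chronic and tolerant users, and entry needs only 72 hours of opioids. All of this stands. It limits what can be claimed about the change score, but it does not remove exposure as a candidate confounder, because the suppressed axis is part of the plan's own account of how opioids affect cortisol.

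A reader might infer that heavily exposed patients will show a larger rise whether or not they withdraw, so that the bias favours the hypothesis. The documents do not support this. They give no recovery time for the axis, and persisting suppression would leave the change unaffected and the weaning value lower.

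The plan also deals with the matter in part. Section 5.1.1 compares clinical characteristics by OIWS status, so an imbalance in exposure would be visible. Section 6.2 concedes confounding, says no statistically significant associations can be made and calls the analyses mainly descriptive; section 6.1 calls the cortisol work exploratory. This lowers the stakes, and makes the false-positive rate a weak measure of harm. But a table of characteristics does not correct the cortisol difference, and a descriptive difference carries the same bias as a test. The "etc" in the medication entry could be stretched to cover opioids, yet no listed confounder enters the section 5.1.2 test.

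Lastly, section 4.6 admits that DSM-5 is not validated in the ICU. If it misses true withdrawal, dose partly stands in for the missed cases, and adjustment can remove real signal. That is a reason to show both estimates.

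**Conclusion.** The point holds as a low-cost improvement to an exploratory secondary analysis. Pre-wean ICU opioid exposure is tied to OIWS risk by the plan and to cortisol by a mechanism that the plan reports as postulated. It is already recorded, yet it is absent from the cortisol confounders and from the comparison. The case is most direct for basal cortisol. For the weaning and change values the bias is possible, and for change its sign is not established.

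Under the assumed positive dose–change correlation (0.2 to 0.6) and odds ratio (1.5 to 2.5 per SD), the spurious difference in change is about 0.1 to 0.5 SD and the false-positive rate about 6% to 21%, mostly below 10%. These are conditional ranges, not estimates for this study. It would go too far to say that the plan states suppression by days of ICU opioids as fact, or that a positive cortisol result would be explained by exposure.

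**What to change.** In section 4.4.2, add cumulative pre-wean opioid dose (fentanyl equivalents, µg/kg) to the cortisol confounders.

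In section 5.1.2, report the OIWS-positive minus OIWS-negative difference in basal, weaning and change in cortisol, each with a confidence interval. Give each one unadjusted and, beside it, adjusted in a linear model for that single exposure measure, with its scale fixed in advance. With about 7 or 8 OIWS-positive patients, one covariate is a sensible limit.

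Label both sets as exploratory. State that other listed confounders, such as sepsis and illness severity, remain unadjusted, and that adjustment may remove some real withdrawal signal because DSM-5 is not validated in the ICU.

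The cost is SAP wording, one degree of freedom, and a somewhat wider interval if dose and OIWS are strongly related. No new data are needed.
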